6. STATISTICAL ANALYSIS

• General

All measured variables and derived parameters will be listed individually and, if appropriate, tabulated by descriptive statistics.

For categorical variables, summary tables will be provided giving sample size, absolute and relative frequency by study group. Confidence intervals (95% degree of confidence) for proportions will be presented for selected endpoints.

For continuous variables, summary tables will be provided giving sample size, arithmetic mean, standard deviation, coefficient of variation (CV%), median, minimum and maximum and 95% CI (Confidence Interval) for means of variables by study group.

All tests will be two-tailed, and a p value of 5% or less will be considered statistically significant.

The data will be analyzed using the SAS ® version 9.4 (SAS Institute, Cary North Carolina).

Statistical methods presented in the SAP may be slightly different from those that are presented in the protocol. Differences are clearly stated and the SAP supersedes the protocol only with regard to the way data will be handled and analysed.

• Subject Disposition

A detailed description of subject accountability including count of subjects included, exposed, completed (i.e., subjects who complete the study treatment) and discontinued along with the main reason for discontinuation will be generated for each study arm (Chinese vs. non-Chinese) and for all subjects. All withdrawals from the study will be fully documented in the body of the Clinical Study Report.

Medi Stat	DOCUMENT NUMBER: 140-BST-PLN-001	page: 15 of 20
TITLE: Statistical Analysis Plan	of Protocol Number RZL-012-SMFC-P2US-001	EFFECTIVE DATE : 03/08/2022 REVISION NUMBER : 1.0

• Demographic and Baseline Characteristics

Baseline will be defined as the last available and evaluable parameter value before and closest to the injection. If a rechecked value is used for baseline, it should be collected under the same conditions as for the planned baseline.

Baseline data including demographics, weight, height, BMI, prior medications, medical history and pregnancy tests will be listed and tabulated with the appropriate descriptive statistics by study arm and for all subjects in ITT population.

Baseline safety data such as vital signs, ECG, safety laboratory assessments and physical examination will be presented along with subsequent safety values assessed during or after injections.

- Analysis of Primary Endpoint
 - The characterization of RZL-012 pharmacokinetic (PK) profile and comparison in a Chinese vs. a non-Chinese population

The following parameters will be evaluated for RZL-012 injection treatment for every subject:

- C_{max}: Maximum measured plasma concentration over the time span specified.
- T_{max} : Time to maximum measured plasma concentration. If the maximum value is observed at more than one time point, T_{max} will be defined as the first time point observed with this value.
- AUC_{0-t}: The area under the plasma concentration versus time curve, from time 0 to the last measurable concentration, as calculated by the linear trapezoidal method.
- AUC_{0-inf}: The area under the plasma concentration versus time curve from time 0 to infinity. AUC_{0-inf} is calculated as the sum of AUC_{0-t} and the ratio of the last measurable plasma concentration to the elimination rate constant.
- $k_{el}(\lambda_z)$: Apparent first-order terminal elimination rate constant calculated from a semilog plot of the plasma concentration versus time curve. The parameter will be calculated by linear least-squares regression analysis using the maximum number of points in the terminal log-linear phase. (e.g., three or more non-zero plasma concentrations).
- T₂: Apparent first-order terminal elimination half-life will be calculated as 0.693/k_{el}.
- C_{last} / λ_z : C_{last} is the last measurable concentration.

Other pharmacokinetic parameters may be calculated if deemed necessary.

Medi Stat	document number: 140-BST-PLN-001	page: 16 of 20
TITLE: Statistical Analysis Plan	of Protocol Number RZL-012-SMFC-P2US-001	EFFECTIVE DATE: 03/08/2022 REVISION NUMBER: 1.0

A total of 10 subjects per group will be used to compare between PK profile of both populations.

PK assessments will be compared between the 2 study populations. The individual values of for RZL-012 plasma concentration and evaluated PK parameters will listed by subject.

Summary tables will be generated for RZL-012 concentration by time point and for all derived PK parameters presenting sample size (N), mean, Standard deviation, Standard Error, Median, minimum and maximum values, Coefficient of variation (CV%) and 95% CI (Confidence Interval) for means by study arm.

Graphical displays will be generated presenting mean concentration by study arm as well as individual graphs per subject.

• Analysis of Safety Endpoints (Exploratory)

Safety data will be summarized by study arm. Descriptive statistics will be provided for actual values and change from baseline values for vital signs, safety laboratory assessments, physical examinations, blood parameters, ECG.

• Adverse Events (AEs)

AEs will be coded using MedDRATM and will be presented by body system. AEs will be graded according to the Common Terminology Criteria for Adverse Events (CTCAE) v 5.0.

AE assessment and treatment area evaluation including, but not limited to evaluation of edema, pain, bruising, erythema, induration, numbness, paresthesia, tenderness, and pruritus.

AE data will be listed individually including the nature, body system, seriousness, severity and relationship of AEs to study drug.

The incidence of AEs and percentage of patients experiencing AEs will be tabulated by the nature of AEs (all AEs, Serious AEs (SAEs), Severe AEs AEs related to study drug, AEs that led to study/treatment discontinuation) for each study arm. Different features may be crossed such as severity and relationship to study drug to provide additional percentages.

The incidence and percentage of patients experiencing AEs will also be summarized by SOC and by PT within a system organ class and further by severity and relationship to treatment if needed for each study arm.

Serious adverse events (SAEs) will be described in narratives as part of the study report.

Medi Stat	DOCUMENT NUMBER: 140-BST-PLN-001	page: 17 of 20
TITLE: Statistical Analysis Plan	of Protocol Number RZL-012-SMFC-P2US-001	EFFECTIVE DATE : 03/08/2022 REVISION NUMBER : 1.0

• Skin irritancy

Skin irritancy AEs related to the injection procedure will be evaluated for frequency, severity and duration by treatment group.

Fisher's Exact test will be applied for testing the statistical significance of the difference in percent of subjects that experienced Skin irritancy AEs related to the injection procedure between the study groups.

• Safety Laboratories

All safety laboratory parameters will be summarized using continuous variable descriptive statistics where applicable. Changes and relative changes from baseline will be calculated and summarized as well.

The normal/abnormal status and clinical significance of observations will be summarized using counts and percentages per study arm and per visit.

• Vital Signs

All vital signs will be summarized using continuous variable descriptive statistics where applicable. Changes and relative changes from baseline will be calculated and summarized as well.

• ECG

ECG results will be summarized in appropriate tables using descriptive statistics by study arm. Changes from baseline values will be summarized as well to indicate if there has been any change.

• Analysis of Efficacy Endpoints (Exploratory)

The exploratory endpoints will be analyzed as follows:

• The proportion of subjects in each population who have at least a 1-grade improvement in the C-CAT on Day 84 versus baseline will be calculated and summarized by study arm along with 95% CIs for proportions (Fisher's Exact method).

Medi Stat	document number: 140-BST-PLN-001	page: 18 of 20
TITLE: Statistical Analysis Plan	of Protocol Number RZL-012-SMFC-P2US-001	EFFECTIVE DATE : 03/08/2022 REVISION NUMBER : 1.0

A two-sided test of equality of binomial proportions will be applied for testing the statistical significance of the difference in percent of subjects who have at least a 1-grade improvement in the C-CAT on Day 84 versus baseline between study arms.

• The proportion of subjects in each population who have at least a 1-grade improvement in the S-CAT on Day 84 versus baseline will be calculated and summarized by study arm along with 95% CIs for proportions (Fisher's Exact method). A two-sided test of equality of binomial proportions will be applied for testing the statistical significance of the difference in percent of subject who have at least a 1-grade improvement in the S-CAT on Day 84 versus baseline.

• The proportion of subjects in each population who have at least a 1-grade improvement in both the C-CAT and S-CAT on Day 84 versus baseline will be calculated and summarized by study arm along with 95% CIs for proportions (Fisher's Exact method).

A two-sided test of equality of binomial proportions will be applied for testing the statistical significance of the difference in percent of subject who have at least a 1-grade improvement in both the C-CAT and S-CAT on Day 84 versus baseline.

• The proportion of subjects in each population who have at least a 2-grade improvement in both the C-CAT and S-CAT on Day 84 versus baseline will be calculated and summarized by study arm along with 95% CIs for proportions (Fisher's Exact method).

A two-sided test of equality of binomial proportions will be applied for testing the statistical significance of the difference in percent of subject who have at least a 2-grade improvement in both the C-CAT and S-CAT on Day 84 versus baseline.

• SMF thickness measured with caliper will be summarized by study visit (Screening, Day 28, Day 56, Day 84) and by study arm using continuous descriptive statistics. Change and relative change from baseline will be calculated and tabulated in the same manner.

The Paired T-test or Signed rank test for two means (paired observations) (as is appropriate) will be applied for testing the statistical significance of the reduction (change and relative change from baseline) in SMF thickness measured with caliper (Day 84 versus baseline) in each study arm.

The two-sample T-test or Non-parametric Wilcoxon-Mann-Whitney Rank sum test for independent samples (as is appropriate) will be applied for testing the statistical significance of the difference in reduction in SMF thickness measured with caliper (Day 84 versus baseline) between Chinese population and non-Chinese population.

Medi Stat	document number: 140-BST-PLN-001	page: 19 of 20
TITLE: Statistical Analysis Plan	of Protocol Number RZL-012-SMFC-P2US-001	EFFECTIVE DATE : 03/08/2022 REVISION NUMBER : 1.0

The additional exploratory endpoints will be analyzed as follows:

The SMF improvement using the Global Aesthetic Improvement Scale (GAIS), the physician Global Assessment of Change Scale, Subjects Global Self-Assessment of Change Scale, Subject's Global Assessment of Change Scale, the subject's satisfaction questionnaires, and the subject's impact questionnaire will be summarized at each timepoint and by study group.

• The physician global assessment will be summarized using categorical descriptive statistics by study visit for each study arm. Shift from baseline will be evaluated and tabulated in the same manner.

• The Physician Global Assessment Improvement Scale (GAIS) will be summarized using categorical descriptive statistics by study visit for each study arm.

• The Subject Global Self-Assessment scale will be summarized using categorical descriptive statistics by study visit for each study arm. Shift from baseline will be evaluated and tabulated in the same manner.

• The Subject Global Assessment of Change Scale will be summarized using categorical descriptive statistics by study visit for each study arm.

• Subject's satisfaction questionnaires answers will be summarized using desciptive statistics by study visit for each study arm. Shift from baseline will be evaluated and tabulated in the same manner.

Two Subject satisfaction binary variables will be defined for every subject in the ITT population based on the satisfaction questionnaire for each one of the questions:

- 1. Subjects who at any point in time answered "Extremely Satisfied" or "Satisfied" (Grades 0,1).
- 2. Subjects who at their last assessment answered "Extremely Satisfied" or "Satisfied" (Grades 0,1).

Subjects with no assessment will be considered as non-responders. The proportion of satisfied subjects (according to said binary variables) will be calculated along with 95% exact confidence intervals for each treatment group. Fisher's Exact test will be applied for testing the statistical significance of the difference in percent of satisfied subjects between treatment groups.

• SMF improvement using Subject's Impact Questionnaire answers will be summarized using descriptive statistics by study visit for each study arm. Shift from baseline will be evaluated and tabulated in the same manner.

Medi Stat	document number: 140-BST-PLN-001	PAGE: 20 of 20
TITLE: Statistical Analysis Plan	of Protocol Number RZL-012-SMFC-P2US-001	EFFECTIVE DATE : 03/08/2022 REVISION NUMBER : 1.0

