3.2 Study Endpoints

3.2.1 Primary Endpoint

The pharmacokinetic profile of RZL-012 will be compared in a Chinese vs. a non-Chinese population based on:

- C_{max} Maximum concentration achieved.
- T_{max} Time to reach maximum concentration (hours).
- AUC_{last} The area under the concentration vs. time curve, calculated as sum of AUCs using linear trapezoidal summation from time 0 to the last measurable data point.
- AUC_{partial} The area under the concentration vs. time curve, calculated as sum of AUCs using linear trapezoidal summation from time 0 to the maximal measurement (T_{max}).
- $\lambda_{z \text{ (Lambdaz)}}$ Individual estimate of the terminal elimination rate constant, was calculated using log-linear regression of the terminal portions of the plasma concentration-versus-time curves.
- AUC_{inf} The area under the plasma concentration-time curve extrapolated to infinity,

calculated as:

AUC_{last} + Clast/ λz , where C_{last} is the last measurable concentration.

• $T_{1/2}$ - Apparent terminal elimination half-life time (hours), defined as $0.693/\lambda z$.

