4.0 STUDY DESIGN

4.1 Overall Design

This is a Phase 2, open-label study that will consist of a screening period, baseline period in which subjects will receive a single treatment session of RZL-012 and a follow-up period. The single treatment session will consist of multiple injections of RZL-012 into the submental area under the chin. Blood samples will be collected from all subjects for PK analyses in the first 48 hours after dosing. Subjects will thereafter be monitored for safety and efficacy for at least 84 days.

All subjects will be treated with a total dose of 270 mg RZL-012.

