8.6 Pharmacokinetics

Blood samples for testing of RZL-012 pharmacokinetics will be taken from all subjects at the baseline visit prior to injection, at 30 and 60 minutes post dosing and at 2h, 3h, 4h, 6h, 8h, 24h, 30 and 48 hours post injection.

Each sample (10 mL each) will be collected in K₂EDTA vials which will be stored on an ice block or wet ice until centrifuged with 60 minutes of collection. Samples will be centrifuged at 1200 g in 4 °C for 10 minutes. Plasma will be removed and placed in aliquots (4 aliquots of 1 mL each) within 20 minutes of centrifugation and flash frozen on dry ice. Processed samples will be placed in frozen (-60 to -90 °C) storage. Levels of RZL-012 in K₂EDTA human plasma will be determined using a validated method of Liquid Chromatography-Tandem Mass Spectrometry. Two aliquots from each time point will be retained for possible future analysis from all subjects

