- AUC_{inf} The area under the plasma concentration-time curve extrapolated to infinity, calculated as:

AUClast + Clast/ λz , where Clast is the last measurable concentration.

• $T_{1/2}$ - Apparent terminal elimination half-life time (hours), defined as $0.693/\lambda z$.

Exploratory Endpoints:

- Comparison of the proportion of subjects in each population who have at least a 1-grade improvement in the C-CAT on Day 84 versus baseline.
- Comparison of the proportion of subjects in each population who have at least a 1-grade improvement in the S-CAT on Day 84 versus baseline.
- Comparison of the proportion of subjects in each population who have at least a 1-grade improvement in both the C-CAT and S-CAT (Day 84 versus baseline).
- Comparison of the proportion of subjects in both populations who have at least a 2-grade improvement in both the C-CAT and S-CAT (Day 84 versus baseline).
- Comparison of the reduction in SMF thickness measured with caliper (Day 84 versus baseline) in a Chinese vs. non-Chinese population
- Safety of RZL-012 in the treatment of SMF reduction.

Statistics in Medicine	DOCUMENT NUMBER: 140-BST-PLN-001	PAGE: 9 of 20
TITLE: Statistical Analysis Plan of Protocol Number RZL-012-SMFC-P2US-001		EFFECTIVE DATE : 03/08/2022 REVISION NUMBER : 1.0

- Physicians Global Assessment
- SMF improvement using the Global Aesthetic Improvement Scale (GAIS).
- Subject Global Self-Assessment
- SMF improvement using the Subject Global Assessment of Change Scale.
- SMF improvement using the subject's satisfaction questionnaires.
- SMF improvement using Subject's Impact Questionnaire.
- Study Design

This is a Phase 2, open-label study that will consist of a screening period, baseline period in which subjects will receive a single treatment session and a follow-up period. The single treatment session will consist of multiple injections of RZL-012 for a maximal total dose of 270 mg into the submental area under the chin. Blood samples will be collected from all subjects for PK analyses in the first 30 hours after dosing. Subjects will thereafter be monitored for safety and efficacy for at least 84 days.

20 adult volunteers (10 Chinese and 10 non-Chinese) whose age is within 18 to 65 years who have consented to participate in this study and seek submental fat reduction will be enrolled into the study.

All subjects will receive a single multi-injection session of RZL-012 in accordance with the table below:

[figure not shown]
Number of subjects	N=20

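### The linear trapezoidal rule across the 8 to 24 h sampling gap can overstate AUC by an elimination-dependent amount, and so distort the AUC ratio between populations if their elimination differs

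*SAP*

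**What the plan says.** The SAP's analysis of the primary endpoint (section 6) takes AUC0-t "from time 0 to the last measurable concentration, as calculated by the linear trapezoidal method". Protocol section 3.2.1 has the same rule for AUClast, "calculated as sum of AUCs using linear trapezoidal summation from time 0 to the last measurable data point", and the protocol synopsis and the endpoint list in SAP section 5 agree. AUC0-inf "is calculated as the sum of AUC_{0-t} and the ratio of the last measurable plasma concentration to the elimination rate constant", so it inherits any error in AUC0-t. Neither document provides a logarithmic rule or a sensitivity analysis for the integration method.

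Protocol section 8.6 takes blood before dosing and then "at 30 and 60 minutes post dosing and at 2h, 3h, 4h, 6h, 8h, 24h, 30 and 48 hours post injection". The longest interval before 30 h is therefore the 16 hours from 8 to 24 h. The documents disagree on the PK window: SAP section 5 (like the synopsis) has "PK analyses in the first 30 hours after dosing", while Protocol section 4.1 says "Blood samples will be collected from all subjects for PK analyses in the first 48 hours after dosing". That needs reconciling in its own right, but the 8 to 24 h gap exists under both.

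The elimination rate constant comes from log-linear regression "using the maximum number of points in the terminal log-linear phase". On the comparison itself the SAP says only that "PK assessments will be compared between the 2 study populations".

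**The concern.** The two parts of the calculation do not fit together. The elimination constant is estimated on the premise that concentrations fall exponentially, while AUC over the same part of the curve is computed as if they fell in a straight line. A chord between two points on an exponential decline lies above the curve, and 16 hours is long enough for this to matter.

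Sharing a schedule does not protect the comparison. The overstatement depends on the elimination rate, so it cancels from the AUC ratio only if both populations eliminate the drug at the same rate. The primary objective is a PK comparison in a bridging study, and half-life and the elimination constant are among the compared parameters. If they differ, part of the AUC contrast would reflect the integration rule.

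**Working it through.** The plan states no half-life, AUC or expected difference, so there is no figure to reproduce.

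**Inputs from the documents.** Integration rule (SAP section 6); sampling times 0, 0.5, 1, 2, 3, 4, 6, 8, 24, 30, 48 h (Protocol section 8.6); AUC0-inf = AUC0-t + Clast/λz.

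**Assumptions, not in the documents.** One compartment with first-order absorption, C(t) = ka/(ka − k) × (e^(−kt) − e^(−ka·t)), k = ln 2 / half-life, unit dose/volume; ka 0.5 to 2 per h; no assay noise; λz from the last three measurable points; quantification limit zero, 1% or 5% of Cmax.

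**Step 1: the gap alone.** For exponential decline over 16 h, linear/true = (x/2)·coth(x/2), with x = 16 × ln 2 / half-life. At 6 h, x = 1.848 and the ratio is 1.27. The overstatement is 7% at 12 h, 15.5% at 8 h, 27% at 6 h, 57% at 4 h and 94% at 3 h.

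**Step 2: the whole curve, one case.** Half-life 6 h, ka = 1 per h: k = 0.1155, C(8) = 0.448, C(24) = 0.0707. Linear area over the gap = 16 × (0.448 + 0.0707)/2 = 4.15, against a true 3.27. Over 0 to 48 h the linear total is 9.56 against a true 8.62, or +10.9%. Linear-up/log-down gives 8.57, or −0.6%.

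**Step 3: AUClast bias by half-life** (ka 0.7 to 1.5 per h, last sample 30 or 48 h, all measurable).

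| Half-life | Linear rule |
|---|---|
| 12 h | +3.1 to +4.0% |
| 8 h | +6.4 to +7.6% |
| 6 h | +9.7 to +11.3% |
| 4 h | +14.7 to +17.3% |
| 3 h | +16.5 to +20.4% |

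Linear-up/log-down is no worse than −1.3% over these half-lives. The linear bias does not keep rising: for AUCinf at ka = 1 it is +18.3% at 3 h, +16.4% at 2 h, +11.8% at 1.5 h and +4.8% at 1 h, because little of the total AUC then remains after 8 h.

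**Step 4: the ratio.** Reported ratio = true ratio × (1 + bias in slower arm)/(1 + bias in faster arm). For 4 vs 6 h: 1.50 × 1.109/1.161 = 1.43. For a true AUCinf ratio of 1.50 due to elimination alone (ka = 1, all samples measurable):

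| Half-lives | Linear rule reads |
|---|---|
| 24 vs 36 h | 1.492 |
| 12 vs 18 h | 1.470 |
| 8 vs 12 h | 1.449 |
| 6 vs 9 h | 1.436 |
| 4 vs 6 h | 1.432 |
| 3 vs 4.5 h | 1.454 |
| 2 vs 3 h | 1.525 |
| 1.5 vs 2.25 h | 1.579 |

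The lowest reading over ka 0.5 to 2 is about 1.42. Linear-up/log-down gives 1.503 for 6 vs 9 h and 1.501 for 12 vs 18 h. A 1.25-fold bioavailability difference with equal half-lives reads exactly 1.25 under the linear rule.

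**Step 5: quantification limit.** AUC0-t stops at the last measurable sample. Take 4 vs 6 h, ka = 1, limit 5% of Cmax. At 4 h, C(24) = 0.0189 against Cmax 0.692 (2.7%): not measurable, so the gap is not integrated and the AUClast error is about −1%. At 6 h, C(24) = 0.0707 against Cmax 0.744 (9.5%): measurable, so the gap is integrated. The linear AUCinf ratio reads 1.63 for a true 1.50. With a limit of 1% of Cmax, 3 vs 4.5 h reads 1.70.

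**The case against.** The linear rule is fully specified and consistent across both documents, so this is partly a choice between methods. The elimination difference that drives the distortion is estimated separately through λz and half-life, which the trapezoidal rule does not touch. Individual concentrations will be listed, so AUC can be recomputed later. The attenuation is also small against the study's precision. With 10 per arm and an assumed between-subject CV of 30 to 50%, the log-scale SD is √ln(1 + CV²) = 0.294 to 0.472, and the 95% interval for a ratio is a factor of exp(2.101 × SD × √(2/10)) = 1.32 to 1.56 either way. The SAP says any p-values are only to establish trends, and no AUC margin exists that this error could push across a boundary.

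All of that limits the importance of the point. It does not make the linear AUC accurate, and reporting half-life beside it does not repair the AUC values or their ratio.

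A reader might go further and infer that the rule always shrinks the difference between populations. The documents do not support this. A bioavailability difference passes through unchanged; at half-lives below about 2 to 3 h the ratio can widen; and if only one population has a measurable 24 h sample, the difference can be exaggerated. Even where the ratio shrinks, the arithmetic difference in AUCinf falls by at most about 5% over the assumed range, and can grow. Without a half-life or a quantification limit, neither direction nor size can be settled from the plan.

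**Conclusion.** The point holds conditionally. If the 24 h sample is measurable and decline is roughly exponential, the specified rule overstates AUC0-t and AUC0-inf by an elimination-dependent amount. In the assumed model this ranges from a few per cent at a half-life of 12 h to about a fifth at 3 h. Equal elimination in the two populations removes the effect from the ratio. Unequal elimination leaves a distortion, typically attenuation of about 2 to 5% in the AUCinf ratio for faster half-lives of 3 to 12 h (1.470/1.50 = 0.98; 1.432/1.50 = 0.955). In the less typical cases the ratio is inflated, by up to about 13% in the mixed-measurability example (1.70/1.50). These sizes rest on one-compartment kinetics, the assumed absorption rates and noise-free data. Severity is low to moderate: a cheap improvement, not a flaw that invalidates the comparison.

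**What to change.** In the SAP's analysis of the primary endpoint, specify linear-up/log-down for AUC0-t and AUC0-inf: linear while concentrations rise, logarithmic while they fall. Align the AUC definitions in SAP section 5, the protocol synopsis and Protocol section 3.2.1, and report the linear-rule AUC as a sensitivity analysis. The SAP is to be finalised before hard lock and takes precedence over the protocol on data handling where differences are stated, so the change can be made there first.

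The cost is wording and one extra set of AUC columns; no samples, subjects or procedures are added. If earlier RZL-012 studies used the linear rule, both versions must be shown to keep the comparison with them.

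The change does not correct a poorly estimated λz. With ka = 0.5 per h, half-life 4 h and a last measurable sample at 8 h, the 4, 6 and 8 h concentrations are 0.558, 0.465 and 0.355. Then λz = ln(0.558/0.355)/4 = 0.113 against a true 0.173, and AUC0-inf is too high under either rule. Reporting the extrapolated fraction of AUC0-inf and the points used for λz would make such cases visible.

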8.11 Caliper Measurements

Caliper measurements of submental fat thickness will be taken at screening and at study visits Day 28, Day 56 and Day 84.

To make the measurement, the subject's head should be maintained in a neutral position and the caliper positioned to pinch the skin at 15 mm on either side of the center point of the submental area.

The change from baseline in caliper-measured submental thickness will be calculated as an exploratory efficacy endpoint.

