Study Procedure	Screening Day	Baseline (Treatment)	Visit Schedule (Days 1 to 84)				
Study Day	Day (-28) through Day (-1)	Day 0	Day 1	Day 7	Day 28	Day 56	Day 84
Signed informed consent	Х						
Medical history	Х						
Physical Exam	Х		Х	X			Х
Concomitant Medication	X	Х	Х	Х	Х	Х	Х
Pregnancy β-hCG	Х						
Pregnancy urine test (women)		Х					X
Caliper measurement of submental fat	X				Х	X	Х
Weight measurements	Х	Х			Х	Х	Х
Biochemistry Lab parameters	Х		Х	Х	Х		X
Pharmacokinetics		Х	Х				
ECG	X		Х				Х
Vital signs	Х	Pre X post	Х	X	Х	Х	Х
Injection of RZL- 012		Х					

Medi Stat	DOCUMENT	NUMBER: 140-1	BST-PLN-00	1	PAGE	: 12 of 2	20	
TITLE: Statistical Analysis Plan	of Protocol Numb	per RZL-012-SMF(C-P2US-001				ATE: 03/0 ABER: 1.0	
Clinician Chin Assessment Tool (C-CAT)	X	X			X	Х	X	
Subject- Self-Chin Assessment Tool (S-CAT)	X	x			X	X	X	
Physician Global Assessment Improvement Scale (GAIS) and physician global assessment	X				X	X	X	
Subject's Satisfaction questionnaire for SMF appearance	X				Х	Х	Х	
Subject's impact questionnaire	X				Х	Х	Х	
Subject Global Assessment of Change and subject self assessment	X				Х	Х	х	
2D Standardized photography	X		Х	X	Х	Х	Х	

Х

Х

Х

Х

Х

AEs

Х

Medi Stat	DOCUMENT NUMBER: 140-BST-PLN-001	page: 13 of 20
TITLE: Statistical Analysis Plan	of Protocol Number RZL-012-SMFC-P2US-001	EFFECTIVE DATE : 03/08/2022 REVISION NUMBER : 1.0

• Rationale Sample Size Calculation

20 adult volunteers (10 Chinese and 10 non-Chinese) whose age is within 18 to 65 years who have consented to participate in this study and seek submental fat reduction will be enrolled into the study.

No formal sample size calculation was performed. The planned sample size of 10 subjects per study arm is sufficient to compare the PK profile between the 2 study populations. Any p-value which may be shown in the final report, will be presented only to establish trends.

• Statistical Analysis Software and Data Management

Data manipulation, tabulation of descriptive statistics, calculation of inferential statistics, and graphical representations will be performed using SAS® version 9.4 or higher for Windows. If the use of other software is warranted, the final statistical methodology report will detail what software was used for what purposes.

• Data Management

Data management for the study is performed by Medistat.

Medical Coding

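### The Day 84 efficacy comparisons between Chinese and non-Chinese subjects have no confidence interval for the difference, the responder test is unnamed, and the caliper scale is ambiguous

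*SAP*

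**What the plan says.** Comparing Day 84 efficacy between the two populations is among the secondary objectives (Protocol 3.1.2; SAP section 5, Secondary Objectives). The endpoints that serve it are listed as exploratory.

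SAP section 6, Analysis of Efficacy Endpoints, treats four responder endpoints alike: at least a 1-grade improvement in C-CAT, in S-CAT, and in both, and at least a 2-grade improvement in both. Each gets a proportion with an exact 95% interval by arm, followed by a test: "A two-sided test of equality of binomial proportions will be applied for testing the statistical significance of the difference in percent of subjects". Protocol 9.5 is equally generic. Elsewhere the SAP does name its test for a binary outcome: "Fisher's Exact test will be applied for testing the statistical significance of the difference in percent of subjects that experienced Skin irritancy AEs". It does the same for the satisfaction questionnaire.

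For the caliper, change and relative change are both tabulated, and the within-arm test covers "the reduction (change and relative change from baseline) in SMF thickness measured with caliper (Day 84 versus baseline) in each study arm". The between-population test, a t-test or rank sum test with no rule for choosing, covers "the difference in reduction in SMF thickness measured with caliper (Day 84 versus baseline) between Chinese population and non-Chinese population". Protocol 8.11 says: "The change from baseline in caliper-measured submental thickness will be calculated as an exploratory efficacy endpoint".

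The general text (Protocol 1.1 and 9.3; SAP section 6, General) describes intervals by arm or group, or for proportions on selected endpoints. None of it supplies an interval for a difference.

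On p-values, the SAP's sample size paragraph says: "Any p-value which may be shown in the final report, will be presented only to establish trends". Its General paragraph says: "All tests will be two-tailed, and a p value of 5% or less will be considered statistically significant".

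**The concern.** The efficacy objective is a comparison, but the plan never estimates the compared quantity with its uncertainty. It offers two separate intervals and a p-value. With 10 subjects per arm a large p-value is the likely outcome whether or not the populations respond alike, so the p-value cannot carry the comparison. The two within-arm intervals do not directly give the interval for the difference.

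Two smaller gaps add to this. A test of equality of proportions could be a pooled z (Pearson) test, an unpooled z test or an exact test, and at this size these can fall on opposite sides of 5%. For the caliper, absolute and relative change can give different answers if baseline thickness differs between the populations, and the SAP does not say which one the between-population test uses.

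**Working it through.** **Inputs.** n = 10 per arm and two-sided 5% come from the SAP. The SAP states that no formal sample size calculation was done, so there is no power figure to reproduce. The documents give no C-CAT or S-CAT response rates and no caliper SD, so every rate below is an assumption.

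**1. Interval for a difference in proportions (Newcombe).** With Wilson limits (l1, u1) and (l2, u2) for the two arms and d = p1 - p2:

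- lower = d - sqrt[(p1 - l1)^2 + (u2 - p2)^2]
- upper = d + sqrt[(u1 - p1)^2 + (p2 - l2)^2]

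For 8/10 in both arms the Wilson limits are 0.490 and 0.943, so the half-width is sqrt[(0.800 - 0.490)^2 + (0.943 - 0.800)^2] = sqrt(0.0960 + 0.0205) = 0.341. The interval is -34 to +34 points, with p = 1.0.

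For 10/10 in both arms the Wilson limits are 0.722 and 1, so the half-width is 1 - 0.722 = 0.278. The interval is -28 to +28 points. A Wald interval would collapse here to 0 to 0, which is why the method needs stating.

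For 5/10 in both arms the interval is -37 to +37 points.

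Expected interval width over all outcomes, at assumed equal true rates:

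| True rate in both arms | Expected width (points) |
|---|---|
| 50% | 72 |
| 70% | 70 |
| 80% | 67 |
| 90% | 62 |

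**2. Does the choice of test matter?** The pooled statistic is z = (p1 - p2) / sqrt[pbar(1 - pbar)(2/10)].

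- 9/10 vs 4/10: pbar = 0.65, z = 0.5 / sqrt(0.0455) = 2.34, p = 0.019; Fisher p = 0.057.
- 10/10 vs 6/10: pbar = 0.80, z = 0.4 / sqrt(0.032) = 2.24, p = 0.025; Fisher p = 0.087.

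Over all 11 x 11 = 121 possible tables, the pooled test has p at or below 0.05 in 46 and Fisher in 34. They disagree in 12: 4-0, 6-1, 7-2, 8-3, 9-4, 10-6 and their mirror images. The Newcombe interval excludes zero exactly when the pooled p is at or below 0.05, in all 121 tables. It therefore disagrees with Fisher in those same 12.

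Probability of landing in one of the 12 (binomial, assumed true rates):

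| True rates | Probability |
|---|---|
| 50% vs 50% | 2.9% |
| 70% vs 70% | 2.5% |
| 80% vs 80% | 2.2% |
| 90% vs 90% | 0.8% |
| 80% vs 50% | 12.2% |

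At 80% vs 50%, exact power is 0.25 for the pooled test and 0.13 for Fisher, so a true 30-point difference would usually be missed by either.

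**3. Caliper.** With equal SDs assumed, the 95% half-width for the difference in mean change is t(0.975, 18 df) x sqrt(1/10 + 1/10) = 2.101 x 0.447 = 0.94 SD of the change. On scale: if baseline were 20% thicker in one arm (an assumption), the same absolute reduction would be 20% of the thinner baseline and 20% / 1.2 = 16.7% of the thicker one.

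**The case against.** The strongest reply is that this is already contained. The endpoints are exploratory, p-values are limited to trends, and the SAP admits there was no formal sample size calculation. Nowhere does it say that a non-significant result will be read as similarity. Anyone can compute the difference interval from the two reported counts. All of that is true. It limits the weight of the point but does not answer it: if the aim is description, an interval describes the comparison better than a test, and its method should be fixed in advance because at this size methods differ.

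Three stronger readings are tempting and do not hold.

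- A reader might infer that the caliper comparison has no stated scale at all. The SAP tabulates change and relative change and uses both to explain *reduction* in the within-arm sentence, and Protocol 8.11 names change from baseline. The scale of the between-population test is ambiguous, not absent.
- A reader might infer that the unnamed test often decides the verdict. If the populations respond alike, it does so about 1-3% of the time. The 12% figure belongs to one assumed unequal scenario.
- A reader might infer that naming Fisher, as the SAP does elsewhere, settles the matter. Beside a Newcombe interval it would reproduce the conflicting verdicts on the same six pairs and their mirror images.

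The link to the objectives is also uneven. The S-CAT-alone comparison is an objective in Protocol 3.1.2 but not in the synopsis or SAP, and the combined objective speaks of determining, not comparing, efficacy.

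**Conclusion.** The point holds as a worthwhile, inexpensive improvement to the exploratory efficacy analysis. No interval for the between-population difference is planned for the four responder endpoints or the caliper, the responder test is unnamed, and the caliper sentence does not say which scale is compared. These are readings of the text and need no assumption.

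Identical observed rates of 8/10 remain compatible with a difference of 34 points either way, and the caliper difference would be known to within about 0.94 SD (equal SDs assumed). Expected widths of 62-72 points and the discordance probabilities rest on assumed response rates.

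The unnamed test and the unqualified 5% sentence would, taken alone, be only missing detail. No figure in the documents is wrong, and the primary PK analysis is not touched.

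**What to change.** Change the SAP only:

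1. For each of the four responder endpoints, report the Chinese minus non-Chinese difference with a 95% small-sample interval, such as Newcombe, as the lead comparative result. Keep the per-arm intervals.
2. Either drop the p-value or keep it as descriptive, in line with the SAP's own sample size paragraph, and from one named test. The pooled test is preferable beside Newcombe because the two always agree at 10 vs 10. If Fisher is used, state that the interval leads.
3. For the caliper, make absolute change from baseline the between-population scale, as in Protocol 8.11, with relative change as a supplement. Report a t-based 95% interval for the difference in mean change whichever test is run.

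The SAP allows for this: "Differences are clearly stated and the SAP supersedes the protocol only with regard to the way data will be handled and analysed". Any departure from the protocol's alpha = 0.05 wording should be recorded there as a stated difference.

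The cost is SAP wording and a few table rows, with no new data, visits or subjects. The downside is that wide intervals will be shown openly.
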